6 STUDY PERIODS, TREATMENT REGIMENS AND POPULATIONS FOR ANALYSES

6.1 Study Periods

[figure not shown]
6.1.1 Baseline Period

Baseline evaluations or events will be defined as evaluations or events that occur before the date and time of the first dose of study treatment (or date of randomization in case of no treatment).

In cases where the time (onset time of event or evaluation time and dosing time) is missing or not collected, the following definitions will apply:

- Pre-treatment AEs will be defined as AEs with an onset date prior to but not including the day of the first dose of study treatment
- Baseline evaluations (laboratory tests, pulse oximetry and vital signs) will be defined as evaluations with a date on or prior to the day of first dose of study treatment

If there are multiple valid assessments, the assessment that is closest to day (and time if collected) of the first dose of study treatment will be used as the baseline in the analyses. If multiple assessments are collected at the same date (and time if collected), the assessment with the latest database entry date (and time if collected) will be considered as baseline.

6.1.2 **Post Baseline Period**

On-treatment AEs will be defined as AEs with an onset date-time on or after the date-time of the first dose of study treatment (or with an onset date on or after the day of first dose of study treatment if time is not collected or is missing). An AE will be counted as on-treatment if the event occurred within 30 days (or 100 days depending on analysis, see Core Safety SAP⁽⁶⁾) of the last dose of study treatment. 30 day and 100 day cut-off is only for subjects off-treatment and no ‘subtracting rule’ will be applied to AEs that occurred pre-treatment.

On-treatment evaluations (laboratory tests, pulse oximetry and vital signs) will be defined as evaluations taken after the day (and time, if collected and not missing) of first dose of study treatment. An evaluation will be counted as on-treatment if it occurred within 30 days (or 100 days depending on analysis) of the last dose of study.

6.2 **Treatment Regimens**

The treatment group “**as randomized**” will be retrieved from the IVRS system

- Arm RT+TMZ: Radiotherapy + Temozolomide
- Arm RT+TMZ+N: Radiotherapy + Temozolomide + Nivolumab

The treatment group “**as treated**” will be the same as the arm as randomized by the IVRS. However, if a subject received the incorrect drug for **the entire period** of treatment, the subject’s treatment group will be defined as the incorrect drug the subject actually received.

6.3 **Populations for Analyses**

- All Enrolled subjects: All subjects who signed an informed consent form and were registered into the IVRS.
- All Randomized subjects: All enrolled subjects who were randomized to any treatment arm. This is the primary dataset for analyses of efficacy parameters and baseline characteristics.
- All Treated subjects: All randomized subjects who received at least one dose of study drug. This is the primary dataset for safety and exposure analyses.

- All Randomized subjects with no baseline corticosteroids: Randomized subjects who did not take corticosteroids for at least 5 days prior to start of dosing (or randomization for subjects not treated).
- Response evaluable subjects: Randomized subjects with measurable lesions at baseline

7 STATISTICAL ANALYSES

7.1 General Methods

Unless otherwise noted, the titles in the following subsections describe tabulations of discrete variables, by the frequency and proportion of subjects falling into each category, grouped by treatment (with total). Percentages given in these tables will be rounded and, therefore, may not always sum to 100%. Continuous variables will be summarized by treatment group (with total) using the mean, standard deviation, median, minimum and maximum values. If a missing category is not being presented in the data display, only those subjects with non-missing values for the parameter being assessed are included in the percentage calculation.

Time to event distributions (i.e. progression free survival, overall survival, time to response and duration of response) will be estimated using Kaplan Meier techniques. When appropriate, the median along with the corresponding log-log transformed 95% CI will be estimated. Rates at fixed timepoints (e.g. OS at 24 months) will be derived from the Kaplan Meier estimate along with their corresponding log-log transformed 95% confidence intervals⁷. Confidence intervals for binomial proportions will be derived using the Clopper-Pearson method⁸.

Unless otherwise specified, the stratified log-rank test will be performed to test the comparison between time to event distributions (OS and PFS). Stratification factor (complete resection or partial resection at baseline) will be as entered into the IVRS.

Unless otherwise specified, the stratified hazard ratio between 2 groups along with CI will be obtained by fitting a stratified Cox model with the group variable as unique covariate. Stratification factor (complete resection or partial resection at baseline) will be as entered into the IVRS.

P-values other than those provided for the PFS and OS primary analysis are for descriptive purpose only and not adjusted for multiplicity.

7.2 Study Conduct

7.2.1 Accrual

The accrual pattern will be summarized per country, investigational site, and per month for all enrolled and randomized subjects. By subject listing of randomization date, first dosing date, country, investigational site will be provided.

7.2.2 Relevant Protocol Deviations

The following programmable deviations will be considered as relevant protocol deviations and summarized by treatment group for all randomized subjects. Non-programmable relevant eligibility and on-treatment protocol deviations, as well as significant (both programmable and non-programmable) eligibility and on-treatment protocol deviations will be reported through ClinSIGHT listings.

At Entrance:

- Subjects receiving prior treatment for GBM other than Surgery
- Subjects with un-methylated MGMT status (using central lab)

- Subjects with KPS < 70
- Subjects on > 20 mg prednisone or > 3 mg dexamethasone at the time of randomization.
- Subjects with start of treatment more than 52 days after surgery
- Subjects without baseline MRI scan

On-study:

- Subjects receiving anti-cancer therapy other than study therapy while on study therapy
- Subjects treated different than as randomized

Listings will also be provided.

7.3 Study Population

Unless otherwise specified, the following analyses will be presented by treatment group as “randomized” for all randomized subjects.

7.3.1 Subject Disposition

The total number of subjects enrolled (randomized or not randomized) will be presented along with the reason for not being randomized.

Number of subjects randomized but not treated along with the reason will be tabulated by treatment group as randomized.

Number of subjects who discontinued study treatment along with corresponding reason will be tabulated by treatment group as treated. Reason for discontinuation will be derived from subject status CRF page.

A subject listing for all treated subjects will be provided showing the subject’s randomization date, first and last dosing date, off treatment date and reason for going off-treatment. A subject listing for all enrolled subjects will also be provided, showing the subject’s race, gender, age, consent date and reason for not being randomized (for those who were not randomized).

7.3.2 Demographics and Baseline Characteristics

The following baseline characteristics will be summarized by treatment group. All baseline presentations will identify subjects with missing measurements. Listings will also be provided.

- Age at the time of informed consent (descriptive statistics)
- Age category I (<65, ≥65)
- Age category II (<65, ≥65- <75, ≥ 75)
- Gender (male, female)
- Race (white, black, asian, other)
- Region (US/Canada, Europe, Rest of the World)
- Disease diagnosis (Glioblastoma, Gliosarcoma)
- RPA Class (III, IV, V, Other)

- Type of Surgery (Complete Resection, Partial Resection, Other)
- Baseline Karnofsky performance status (100%, 90%, 80%, ...)
- Weight , BSA (descriptive statistics)
- Gene Promoter Methylation (Methylated, Unmethylated, Indeterminate, Not reported)
- Smoking Status (Current/Former, Never, Unknown, Not Reported)
- Baseline Corticosteroid Use (Based on average corticosteroid use 5 days prior to start of dosing (randomization date for subjects not treated))
- Time from Initial Disease Diagnosis to randomization (in weeks) (Median, Range)
- All lesions (Investigator Tumor Assessments at Baseline): sites of disease, number of disease sites per subject.
- Measurable lesions (Investigator Tumor Assessments at Baseline): Presence of measurable lesions, site of measurable lesion, sum of products of perpendicular diameters of measurable lesion.
- Pre-treatment events: summarized by worst CTC grade presented by SOC/PT
- Medical History

General medical history will only be listed by subject.

7.3.3 Prior Therapy

The following will be summarized by treatment group.

- Prior systemic cancer therapy (yes/no)
- Prior agent received (generic name)
- Prior surgery related to cancer (yes/no)

Prior systemic cancer therapy agents and medication will be reported using the generic name.

A summary table by ATC class and generic name and a by-subject listing will also be provided for prior/current non study medication.

7.3.4 Baseline Examinations

Subjects with abnormal baseline physical exam results will be tabulated by examination criteria (eg neck, cardiovascular, lungs, etc), by treatment group, and by-subject listing will be produced for all measurements.

7.3.5 Discrepancies Between IVRS and CRF Stratification Factors

Summary tables (cross-tabulations) by treatment group for stratification factor will be provided to show any discrepancies between what was reported through IVRS vs. CRF data (baseline).

- Extent of tumor resection: Complete or Partial

7.4 Extent of Exposure

Listings will include all available exposure data. Analyses will be performed by treatment group “as treated” in all treated subjects, unless otherwise specified.

7.4.1 Administration of Study Therapy

The following parameters will be summarized (descriptive statistics) by treatment group:

- Time from randomization and to first dose of study therapy (0 to 3 days, > 3 to 7, > 7 to 14, > 14 to 21, > 21 to 28, > 28)

Nivolumab

Dose (mg) is defined as total Dose administered (mg) and is collected on the CRF.

Cumulative Dose (mg) is sum of all the doses (mg) administered to a subject.

Duration of Treatment (in months): (Last dose date - Start dose date + 1)/30.4327

Relative dose intensity (%): Sum of all relative dose intensity for all cycles/N where N is the number of cycles of nivolumab administered.

For each cycle i:

Cycle duration (i)(wk)= (dose date(i+1)-dose date (i))/7, when ith cycle is not the last.

Cycle duration (i)(wk)= 2, for the last cycle of the induction phase.

Cycle duration (i)(wk)= 4, for the last cycle of the maintenance phase

Dose Intensity for cycle i (mg/wk)=Dose (i)/Cycle duration (i)

Relative Dose intensity for cycle i (%)=(Dose Intensity for cycle i (mg/wk)/ 120(mg/wk))*100

The following parameters will be summarized (descriptive statistics) for subjects treated with nivolumab:

- Number of doses received
- Cumulative dose
- Relative dose intensity (%) using the following categories: < 50%; 50 - < 70%; 70 - < 90%; 90 - < 110%; ≥ 110%.

Duration of nivolumab treatment will be presented using a Kaplan-Meier curve. The last dose date will be the event date for those subjects who are off study therapy. Median duration of treatment and associated 95% CI will be provided. Subjects who are still on study therapy will be censored on their last dose date.

Temozolomide

Duration of Treatment (in weeks): (Dose end date - Dose start date + 1)/7

Dose (mg/m²): total dose administered (in mg)/BSA at baseline (m²). Dose administered in mg at each dosing date is collected on the CRF

Cumulative dose (in mg/m²): sum of all the doses (mg/m²) administered to a subject

The following parameters will be summarized (descriptive statistics) for subjects treated with temozolomide:

- Duration of Treatment (in weeks)
- Cumulative dose (in mg/m²)

Radiotherapy

Duration of radiotherapy (in weeks): (Dose end date - Dose start date + 1)/7

Cumulative dose (in Gy): sum of all the doses (Gy) administered to a subject as per CRF.

The following parameters will be summarized for subjects treated with radiotherapy:

- Duration of radiotherapy (in weeks)
- Cumulative dose (in Gy)
- Number of subject that received less than 90% of planned dose

A by-subject listing of dosing of study medication (record of study medication, infusion details, and dose changes) and a listing of batch numbers will be also provided.

Analysis on extent of exposure will be restricted to the following populations, unless otherwise noted:

- All treated subjects
- All treated subjects without baseline corticosteroid
- All treated subjects in the first 558 subjects from all randomized population

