## **4.5.2 Temozolomide Dosing**

### **4.5.2.1 Temozolomide Dose and Schedule**

Subjects will be administered temozolomide (TMZ, Temodar®) daily during RT and as maintenance therapy for 6 cycles. **TMZ dosing will be performed according to investigator judgment**; the following guidance is drawn from published literature.

TMZ will be dosed at 75 mg/m^2 once per day continuously throughout RT, typically for 42 days and with a maximum of 49 days. See [Table 4.5.2.3-1](#) for dose modifications during concomitant RT+TMZ dosing. After completion of RT, there will be a 4 week break. Subjects will receive 6 cycles of temozolomide daily x 5 days every 28 days. The timing of maintenance TMZ cycles may be adjusted for clinical convenience, eg, to coincide with nivolumab/placebo dosing.

Table 4.5.2.1-1: Dose Levels for Maintenance TMZ Monotherapy		
Dose Level	TMZ Dose in mg/m^2/day	Notes
-1	100 mg/m  /day	Reduction for prior toxicity
0	150 mg/m  /day	Dose during first maintenance cycle
1	200 mg/m  /day	Dose during subsequent maintenance TMZ in absence of TMZ-related toxicity

Source: adapted from Temodar® package insert (PI)

In the first maintenance cycle, TMZ is given at a dose of 150 mg/m^2, and then increased to 200 mg/m^2 in Cycle 2 as follows: If, during the first cycle, all non-hematologic AEs observed were Grade ≤ 2 (except alopecia, nausea and vomiting) and with platelets ≥ 100 x 10^9/L and ANC ≥ 1.5 x 10^9/L, then the temozolomide dose should be escalated to dose level 1, and this dose should be used as the starting dose for subsequent cycles. Doses of TMZ are not precise but are adjusted based on tolerance; rounding of up to 10% is entirely acceptable.

If treatment after Cycle 1 has to be delayed because of ongoing non-hematologic AEs of Grade ≥ 2, then no escalation is possible. If the dose was not escalated at Cycle 2, then the dose should not be escalated in further cycles based on adverse events (see [Table 4.5.2.3-2](#)). If there was a prior dose reduction or discontinuation during the concomitant period with RT, then dose -1 should be the starting dose for subsequent cycles. Table 4.5.2.1-1 describes dose levels during temozolomide maintenance.

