#### **4.5.2.2 Criteria to Start Temozolomide Maintenance Cycles**

Maintenance treatment begins following a 4-week treatment break after RT. TMZ treatment may begin if blood count (obtained within the prior 3 days) shows ANC ≥ 1.5 x 10^9/L, platelet count ≥ 100 x 10^9/L and any Grade ≥ 3 non-hematologic AE (except alopecia) must have resolved to Grade ≤ 1). If AEs persist, treatment should be delayed by 1 week for up to 4 consecutive weeks. If, after 4 weeks of delay, all AEs have still not resolved to ≤ Grade 1: then any further maintenance treatment with temozolomide should be discontinued.

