2 STUDY DESCRIPTION

2.1 Study Design

This is a randomized phase 3 single blind study of temozolomide plus radiation therapy combined with nivolumab or placebo in newly diagnosed adult subjects with MGMT-methylated glioblastoma.

This study will enroll subjects with newly-diagnosed GBM, following surgical resection of the tumor. Tumor tissue will be evaluated for MGMT methylation by a central laboratory assay through the CA209498 study. After enrolling in the CA209498 study, the subjects may enroll in the CA209548 study and begin the screening process while they wait for the MGMT results. The screening number assigned in the CA209498 IVRS will be the same subject number entered by the site to screen the subject into the CA209548 IVRS. Those with a MGMT status of methylated or indeterminate may be eligible to randomize in the CA209548 study. In order to randomize 693 eligible subjects, a total of approximately 780 subjects will be evaluated. For details, see [Section 2.1.1](#).

Subjects with a central laboratory result of MGMT-methylated or indeterminate may continue in the screening phase, in which eligibility for randomization will be documented and baseline demographic and disease information submitted; for details, see Section 2.1.1. A contrast-enhanced MRI should have been obtained within 72 hours post-surgery (within 24 hours

preferred) as part of the initial screening for the CA209498 study. If not obtained at that time, then a MRI must be performed prior to randomization (> 14 days post-op preferred).

When ready to begin study treatment, subjects will proceed to the treatment phase of the study. The treatment phase will consist of an induction phase (chemoradiation therapy) followed by 4 weeks break and maintenance temozolomide therapy; for details, see Table 2.1-1. All subjects who enter the treatment phase, ie, all randomized subjects, will be followed for safety and tolerability, tumor progression and survival. The first on-study contrast-enhanced MRI should be performed 4 weeks (\pm 7 days) after completing radiation therapy, then subsequent scans should be every 8 weeks (\pm 7 days) up to 24 months post randomization, then every 12 weeks until progression regardless of treatment schedule or dose delays. Tumor progression will be assessed using RANO criteria.

For the purposes of this protocol, each cycle duration is 2 weeks until 8 doses of nivolumab/placebo are complete. The remaining subsequent cycles are 4 weeks in duration.

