9 CONTENT OF REPORTS

10 DOCUMENT HISTORY

Table 10-1: Document History

Version Number	Author(s)	Description
1.0	[REDACTED]	Initial version dated 05-Jan-2017
2.0	[REDACTED]	
Section 2 Study Description: Multiple changes we made in section 2 Study description in accordance with the amendments of the protocol, the history of protocol amendments is added on section 2.4.
 
Section 2.1 Study Design: “The treatment phase will consist of an induction phase (chemoradiation therapy) followed by 4 weeks break and maintenance temozolomide therapy” is added to define induction and maintenance phase for exposure analysis.
 
Section 3 Objectives: The section is modified in accordance with the protocol update.
 
Section 4.1 Primary Endpoint(s): two-co-primary endpoints were set in accordance with the protocol update.
 
Section 4.2 Secondary Endpoint(s): Endpoints are modified to 3 secondary endpoints in accordance with the protocol update; sentence “Subjects who die without a reported progression will be considered to have progressed on the date of death” is removed; “PFS will be determined by investigator reported response based on radiographic and clinical findings in accordance with RANO criteria” text in italic is added for clarity; censoring rules in Figure 4.1-1: Graphic Display of PFS Primary Definition were corrected for cases when subjects have PD/death and on-study scans (event and censoring had been mixed up) and when subsequent therapy started before an event (possibility to censor by randomization date is added).

Table 10-1: Document History

Version Number	Author(s)	Description

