3.0	[REDACTED]	
[REDACTED]
 
Multiple editorial changes
 
Section 1: Research hypothesis and schedule of analyses are modified in accordance with the protocol update.
 
Section 2: Table 2.1-1 Study design schematic is modified in accordance with the protocol update.
 
Section 3: Objectives are modified in accordance with the protocol update.
 
Section 4: Primary and secondary endpoints are modified in accordance with the protocol update.
 
Section 5: Sample size considerations are modified in accordance with the protocol update.
 
[REDACTED]
 
Section 7.4: Analysis on TMZ by phase is removed.
 
Section 7.5.2: Statistical analysis on PFS is modified in accordance with the protocol update.
 
Section 7.5.3.4: Statistical analysis on treatment beyond progression is updated.
 
Section 7.5.4: Details on alpha recycling is added.
 
Section 7.5.5: Interim analysis is modified in accordance with the protocol update.
 
[REDACTED]

Table 10-1: Document History

Version Number	Author(s)	Description
		Multiple editorial changes
4.0	[REDACTED]	Section 1, Section 5 and Section 7.5.5 are updated on the change of removing interim analysis for PFS Section 2.5 is added. Section 4.3.7, Section 4.3.8 and Section 4.3.9 are updated on the analysis time window to be consistent with I-O core SAP. Section 7.5.3.2 is updated. Multiple editorial changes
5.0	[REDACTED]	Section 5: Replacing "O'Brien-Fleming" with "Pocock" in order to keep consistency with stopping boundary specified in sections 7.5.4 and 7.5.5 for all randomized population Section 7.5.4: Minor editorial changes on page 42 to add clarity Section 7.5.5: Minor editorial changes on page 43 to add clarity [REDACTED]

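### SAP 7.4.1 sets the length of the last nivolumab cycle by phase words that the SAP defines only for chemoradiation and temozolomide, so read literally a last 240 mg dose given during temozolomide maintenance scores 50% for that cycle

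*SAP*

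**What the plan says.** In the nivolumab block of SAP 7.4.1, a cycle that is not the last runs from one dose date to the next. The last cycle has no next dose date, so the SAP fixes its length: "Cycle duration (i)(wk)= 2, for the last cycle of the induction phase" and "Cycle duration (i)(wk)= 4, for the last cycle of the maintenance phase". Dose divided by cycle length is compared with 120 mg/week, the cycle percentages are averaged over the cycles given, and the result is reported in bands with cut points at 50, 70, 90 and 110%.

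Section 7.4.1 does not say what the two phases mean for nivolumab. The visible definition is in SAP 2.1: "The treatment phase will consist of an induction phase (chemoradiation therapy) followed by 4 weeks break and maintenance temozolomide therapy". The SAP document history, under version 2.0, says that this sentence "is added to define induction and maintenance phase for exposure analysis". Under version 3.0 it records: "Analysis on TMZ by phase is removed".

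SAP 2.1 gives the nivolumab cycle lengths separately, by dose number: "each cycle duration is 2 weeks until 8 doses of nivolumab/placebo are complete", with 4-week cycles afterwards. Protocol 3.1 and 4.5.1.1 place the first 480 mg dose at Cycle 9, Week 17 if there are no delays.

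**The concern.** The last-cycle rule and the nivolumab schedule change over at different times. Temozolomide maintenance starts after chemoradiation and a 4-week break. The nivolumab interval changes only after dose 8. Between those two points a subject is in the maintenance phase as SAP 2.1 defines it but is still on 2-week, 240 mg cycles. If nivolumab stops there, the literal rule spreads a 2-week dose over 4 weeks. If it stops during the break, the subject is in neither phase and no length is given.

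At stake is the relative dose intensity summary for nivolumab-treated subjects. Administration of study therapy remains on the reduced list of analyses for the primary study report (SAP section 1). The literal error goes one way: it understates intensity for subjects who stop late in the 240 mg period. One programmer following SAP 2.1 and another following the nivolumab schedule would obtain different values for the same subject.

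**Working it through.** **Inputs**
- Formulas, 120 mg/week reference and bands: SAP 7.4.1.
- 240 mg every 2 weeks for 8 doses, then 480 mg every 4 weeks: Protocol Table 4.5-1. Cycle 9 starts 2 weeks after Cycle 8: Protocol 3.1.
- First dose 0 to 7 days before radiotherapy starts: Protocol Table 5.1-2.
- Daily temozolomide throughout radiotherapy, "typically for 42 days and with a maximum of 49 days": Protocol 4.5.2.1.
- "Maintenance treatment begins following a 4-week treatment break after RT": Protocol 4.5.2.2.

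**1. The SAP's reference figure.** 240/2 = 120 mg/week and 480/4 = 120 mg/week. Both reproduce the stated 120.

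**2. Timeline with no delays.** Dose k falls on day 1 + 14(k − 1): dose 5 on day 57, dose 6 on day 71, dose 7 on day 85, dose 8 on day 99 and dose 9 on day 113. Temozolomide maintenance starts on day 1 + offset + radiotherapy length + 28.
- Earliest: 1 + 0 + 42 + 28 = day 71.
- Latest: 1 + 7 + 49 + 28 = day 85.

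Doses 7 and 8 are therefore always 240 mg doses given in maintenance. Dose 6 is in maintenance only with the earliest radiotherapy timing and otherwise falls in the break. Dose 5 falls in the break. If 30 weekday fractions take 40 days (an assumption), maintenance can start on day 69, which slightly widens the set of early timings that catch dose 6.

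**3. Score for the last cycle.** By the nivolumab interval: 240/2/120 = 100%. By the phase definition in SAP 2.1: 240/4/120 = 50%.

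**4. Subject value, on schedule, stop at dose n in maintenance.** Literal rule: ((n − 1) × 100 + 50)/n. By the nivolumab interval: 100%.
- n = 6 (earliest timing only): 550/6 = 91.7%
- n = 7: 650/7 = 92.9%
- n = 8: 750/8 = 93.8%

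All stay in the 90-<110% band. For an on-schedule stop in the break, the value depends on which length is chosen: 450/5 = 90.0% or 100% at dose 5, and 91.7% or 100% at dose 6.

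**5. Subject value with one earlier nivolumab delay of d days**, with radiotherapy and temozolomide on time. The delayed cycle scores x = 100 × 14/(14 + d). Literal rule: ((n − 2) × 100 + x + 50)/n. By the nivolumab interval: ((n − 1) × 100 + x)/n.

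| Stop at dose | Delay (days) | x | Literal | By nivolumab interval | Band changes |
|---|---|---|---|---|---|
| 6 | 14 | 50.0 | 500/6 = 83.3% | 550/6 = 91.7% | yes |
| 7 | 7 | 66.7 | 616.7/7 = 88.1% | 666.7/7 = 95.2% | yes |
| 8 | 7 | 66.7 | 716.7/8 = 89.6% | 766.7/8 = 95.8% | yes |
| 8 | 4 | 77.8 | 727.8/8 = 91.0% | 777.8/8 = 97.2% | no |

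A delay also moves later doses. With 14 days, dose 6 falls on day 71 + 14 = 85, which is in maintenance for every radiotherapy timing in step 2. The affected doses are therefore not limited to 7 and 8 once there is a delay.

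**The case against.** The strongest reply is that the intended meaning can be recovered. SAP 2.1 itself gives 2-week nivolumab cycles through dose 8 and 4-week cycles after, so a 4-week cycle 7 or 8 contradicts the same section that supplies the phase definition. The two last-cycle lines sit in the nivolumab block, use the same 2 and 4 weeks, and share a reference that equals both 240/2 and 480/4. The document history under version 2.0 also records a correction to the last-cycle length, so the rule had been looked at. The phase sentence may have been added mainly for the temozolomide by-phase analysis that version 3.0 dropped. Finally, SAP 2.1 refers to a schematic that is not shown in the public text and might label nivolumab periods.

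Most of this stands as evidence of intent. It does not remove the conflict. Section 7.4.1 keys on the phase words and not on dose number, the visible definition points to the chemoradiation and temozolomide timetable, and the history ties that definition to exposure analysis. Nor does it state a length for a last dose in the break under that definition.

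A reader might go further and infer that the reported dose intensity will be wrong, that on-schedule subjects will drop a band, or that the comparison between arms is affected. The documents do not support these. The programmed derivation is not shown. On-schedule stops stay in the 90-<110% band. The summary covers nivolumab-treated subjects only and enters no efficacy test.

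**Conclusion.** The concern holds as an undefined term which, under the only visible definition, gives a wrong score for one cycle. It is a minor point, worth correcting because the correction is nearly free.

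Its size is 50% instead of 100% for a last 240 mg dose given in temozolomide maintenance. This costs an on-schedule subject about 6 to 8 percentage points of relative dose intensity. A band change requires such a stop together with an earlier delay that is long enough. Number of doses, cumulative dose and dose delays are summarized separately, so the underlying exposure stays visible. Overall survival, progression-free survival, type I error and power are untouched.

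The conclusion rests on the visible text, on radiotherapy starting 0 to 7 days after dose 1 and lasting 42 to 49 days, and on a 28-day break. Late radiotherapy, shifted temozolomide cycles or a delayed start of maintenance, all of which the protocol allows, would move the boundaries. The documents do not give the number of subjects who stopped nivolumab in this window.

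**What to change.** Replace the two last-cycle lines in the nivolumab block of SAP 7.4.1 with: *Cycle duration for the last cycle = 2 weeks if the last dose was one of doses 1-8 (Q2W schedule), 4 weeks if it was a later dose (Q4W schedule).* Remove the induction and maintenance wording from that block. Keep the mean over cycles and the 120 mg/week reference as they are.

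This follows the cycle lengths already stated in SAP 2.1 and Protocol 3.1, covers a last dose in the break, and gives 100% for a full last dose in either period. The cost is two SAP lines and one line in the derivation program. It uses dose dates and dose numbers already collected.
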